## 1.3 Rationale for the Proposed Study

### 1.3.1 Rationale for a Perioperative Study in Subjects Eligible for CN/MET

Historical studies have demonstrated the clinical efficacy of CN in association with immunotherapy. In SWOG-8949, advanced RCC subjects treated with CN in addition to interferon-alpha (IFN- $\alpha$ ) had a significant improvement in OS (11 vs 8 months) compared to those treated with IFN- $\alpha$  alone [23]. Similar results were seen in a European Organisation for Research and Treatment of Cancer (EORTC) study (same treatment as SWOG study), with a significant improvement in OS in favor of CN in addition to immunotherapy [24]. The clinical benefit of CN appears to persist in the TKI era as well; results from the International Metastatic Renal Cell Carcinoma Database Consortium showed a median OS of 20.6 months for subjects who underwent CN vs 9.5 months for those who received only systemic therapy [25].

Furthermore, small studies of MET in select patient populations with limited tumor burden, either upfront or as consolidation (in addition to either systemic TKI or immunotherapy), may provide additional clinical benefit [26, 27]. No prospective studies exist, but multiple retrospective analyses, both in the pre-TKI and TKI era, have demonstrated the significant clinical benefit of MET, particularly in cases where a complete (R0) resection could be achieved [28-32].

Finally, the efficacy and safety of perioperative treatment for subjects with metastatic and advanced RCC prior to CN has been shown in multiple prospective studies. Perioperative TKI treatment has demonstrated tumor shrinkage in the range of 13-22%, with a significant proportion of subjects who were previously deemed unresectable able to proceed with surgical resection [27, 33-36]. Just as importantly, there does not appear to be increased risk of overall surgical morbidity or mortality associated with perioperative therapy. One specific concern is the risk of delayed wound healing in subjects receiving TKI therapy; the results of existing studies are conflicting, as some studies have shown delayed wound healing in up to 20-25% of subjects, while other studies have shown no evidence of delayed wound healing.

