##### 2.1.3.2 Scientific

- To explore the relationship between changes in TIIICs and clinical efficacy in subjects with advanced RCC treated with pembrolizumab-based therapy
- To characterize changes in the frequency and number of circulating T cells induced by pembrolizumab-based therapy in subjects with advanced RCC

- To determine the impact of pembrolizumab-based therapy on the composition and phenotype of the tumor microenvironment (including tumor and stromal cells) in subjects with advanced RCC
- To determine whether locally advanced versus metastatic RCC exhibit differences in immune composition or phenotype at baseline and in response to pembrolizumab-based therapy
- To determine the change in T cell repertoire within the tumor and blood induced by pembrolizumab-based therapy in subjects with advanced RCC
- To explore molecular profiles to identify potentially predictive biomarkers for subjects with advanced RCC treated with immunotherapy

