##### Target lesions

All measurable lesions up to a maximum of 10 lesions total (and a maximum of 5 lesions per organ) representative of all involved organs should be identified as target lesions and recorded and measured at baseline. Target lesions will be selected on the basis of their size (lesions with the LD) and their suitability for accurate repeated measurements (either by imaging techniques or clinically). A sum of the LD for all target lesions will be calculated and reported as the baseline sum LD. The baseline sum LD will be used as reference by which to characterize the objective tumor response.

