#### Exploratory endpoints

- The relationship between clinical efficacy (by above measures) and changes in T1ICs (by above measures) will be explored.
- Clinical efficacy: pathologic response rate, R0 resection rate
- The changes in frequency and numbers of circulating T cells will be assessed by flow cytometry.
- Comprehensive assessment will be performed to explore the tumor microenvironment, including for PD-L1 status. Transcriptional profiling of tumor microenvironment

constituents (including T cell subsets, tumor, and stroma) in pre- and post-treatment specimens will be analyzed .

- Changes in the T cell repertoire will be explored via high resolution TCR sequencing, in both blood and tumor specimens.
- Molecular profiling of pre- and post-treatment tumor and normal tissue will be performed to explore biomarkers of response. Neoepitope burden will be assessed.
- Wilcoxon rank-sum test will be used to assess whether there is a relationship between any of the immune cell subsets and objective radiographic response as well as pathologic response. Cox-proportional hazard models will be applied to assess if there is relationship between any of the immune cell subsets and PFS. Parallel analysis will be performed for PD-L1 expression. Wilcoxon rank-sum test will also be used to assess whether the T cell receptor clonality diversity index is different between responders vs. non-responders (defined by objective radiographic response or pathologic response), and between subjects who have progression within 1-year vs. those whose disease has not progressed. Additional analyses of immunocorrelative data are detailed in the procedures manual.

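### The radiographic biomarker tests in section 8.1 use only responder status; a rank analysis of percent change in tumour size, added beside them, would be a cheap exploratory improvement

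*Combined protocol and SAP*

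**What the plan says.** Section 2.1.3.2 lists this scientific objective: "To explore the relationship between changes in TIIICs and clinical efficacy in subjects with advanced RCC". The exploratory endpoints in section 8.1 repeat it: "The relationship between clinical efficacy (by above measures) and changes in T1ICs (by above measures) will be explored".

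For the immune subsets, the named radiographic test is given as: "Wilcoxon rank-sum test will be used to assess whether there is a relationship between any of the immune cell subsets and objective radiographic response". PD-L1 is analysed in parallel. For T cell receptor clonality, the question is whether the diversity index "is different between responders vs. non-responders (defined by objective radiographic response or pathologic response").

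The same paragraph plans analyses that do not use radiographic response. Pathologic response has its own rank-sum test, clonality is compared by progression within one year, and "Cox-proportional hazard models will be applied to assess if there is relationship between any of the immune cell subsets and PFS". It ends: "Additional analyses of immunocorrelative data are detailed in the procedures manual".

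On measurement, section 7.1.4 has the diameters of target lesions summed at baseline: "The baseline sum LD will be used as reference by which to characterize the objective tumor response". Section 7.1.6 defines partial response as a decrease of at least 30% in that sum. Section 6.1.2.4 requires a scan at week 10, after the last preoperative cycle and before surgery.

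**The concern.** A responder versus non-responder comparison discards the order within each group. A subject whose tumour shrinks by 28% and one whose tumour grows by 15% both count as non-responders. If a marker tracks tumour shrinkage in a graded way, the split loses information that the trial already collects. With few responders, the comparison also rests on a handful of subjects.

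The cohorts are small: up to 12 in Cohort A, and 30 (36 with a dose reduction) in each combination cohort. At stake is the chance of seeing a real link between immune markers and tumour shrinkage. Relating immune change to efficacy is a named objective, and section 1.1 gives the mechanisms of response and resistance as the reason for the study.

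**Working it through.** **Plan's own figure.** There is none to reproduce. The protocol gives no alpha, effect size or power for the exploratory tests. The power and type I error in section 8.2.1 belong to the primary endpoint.

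**Inputs from the protocol**
- Cohort size: 30 without dose reduction (8.2.1); 12 in Cohort A (3.2); up to 84 overall (3.2).
- Partial response cut: 30% decrease in summed diameters (7.1.6).
- Response rates: 34% for pembrolizumab alone (1.1) and 59% for pembrolizumab plus axitinib (1.2.2.1). Neither is given as a 9-week rate.

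**Assumptions, because the protocol is silent**
- Two-sided 5%, no multiplicity adjustment.
- Latent correlation between marker and shrinkage of 0.4 to 0.6.
- Preoperative response share of 15% to 59%.

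**Graded model.** Let Y be standardised shrinkage and X = ρY + √(1 − ρ²)·E, with Y and E independent standard normal. A responder has Y above Φ⁻¹(1 − share). For each simulated cohort, test X by responder status (exact Wilcoxon) and test X against Y (Spearman). Power in % at n = 30, from 3,000 runs per row:

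| Responders | ρ | Wilcoxon | Spearman | Difference (points) |
|---|---|---|---|---|
| 15% | 0.4 | 25.9 | 55.0 | 29.1 |
| 15% | 0.5 | 37.6 | 75.7 | 38.1 |
| 15% | 0.6 | 56.1 | 91.6 | 35.5 |
| 34% | 0.4 | 35.9 | 55.0 | 19.1 |
| 34% | 0.5 | 54.1 | 77.3 | 23.2 |
| 34% | 0.6 | 74.6 | 92.4 | 17.8 |
| 59% | 0.4 | 39.3 | 56.1 | 16.8 |
| 59% | 0.5 | 56.9 | 76.4 | 19.5 |
| 59% | 0.6 | 76.0 | 92.3 | 16.3 |

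The difference is 16 to 23 points at the two cited rates. At 15% responders it is 29 to 38 points here, and about 40 with a continuity-corrected normal approximation to the Wilcoxon test.

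**Other sample sizes, ρ = 0.5.** With 24 evaluable pairs and 34% responders, power is 46% against 67%. With 12 subjects (Cohort A) and 34% responders, it is 17% to 21% against about 35%. If cohorts are pooled, the difference at the cited rates is about 10 points at n = 60 and about 4 points at n = 84. A weaker correlation leaves a larger pooled loss, and a stronger one a smaller loss.

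**Threshold model.** Now let X be shifted by d standard deviations in responders only, with no relation to shrinkage within either group (n = 30):

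| Responders | d | Wilcoxon | Spearman | Difference (points) |
|---|---|---|---|---|
| 20% | 0.8 | 34.5 | 18.6 | −15.9 |
| 20% | 1.2 | 63.2 | 35.3 | −27.9 |
| 34% | 0.8 | 46.9 | 33.5 | −13.4 |
| 34% | 1.2 | 81.4 | 61.6 | −19.8 |
| 59% | 0.8 | 51.3 | 37.6 | −13.7 |
| 59% | 1.2 | 84.7 | 69.5 | −15.2 |

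The sign reverses. Over a wider set of runs the planned test is ahead by about 9 to 29 points.

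**The case against.** The strongest objection is the threshold model. If a marker separates responders from non-responders and does nothing else, the planned test is the better one, and by a margin similar to what it loses under the graded model. This stands. It rules out replacing or demoting the planned test, but it does not argue against a second analysis beside it.

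Several other objections also stand in part:

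- **Pooling.** Section 8.1 does not say that these tests are run by cohort. If cohorts are combined, the loss shrinks.
- **Procedures manual.** It may already contain a continuous analysis. A reader might infer that the trial ignores percent change altogether; the available text shows only that the protocol does not plan such an analysis.
- **Scope.** A reader might take the point to cover every biomarker test. The pathologic-response, one-year progression and PFS analyses do not use the radiographic cut.
- **Fit of the 30% cut.** A reader might conclude that most subjects will fall below it, because section 1.3.1 says "Perioperative TKI treatment has demonstrated tumor shrinkage in the range of 13-22" per cent. That figure is for TKI treatment; Cohort A has no TKI and Cohort B adds pembrolizumab. With an assumed SD of 15 to 20, the share reaching 30% runs from 1 − Φ((30 − 13)/15) = 13% to 1 − Φ((30 − 22)/20) = 34%. Neither the SD nor the transfer to these regimens comes from the protocol.
- **Not the same outcome.** RECIST response also uses non-target and new lesions (Table 9), so percent change in target lesions needs a ranking rule and is not a full substitute.

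**Conclusion.** The concern holds in a limited form. The radiographic biomarker tests for immune subsets, PD-L1 and receptor clonality use responder status alone. The percent change behind that status is derivable at no extra cost, and the protocol does not plan to analyse it.

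The loss of 16 to 23 points (up to about 40 at a 15% response share) rests on a graded association with correlation 0.4 to 0.6, an unadjusted two-sided 5% test and 30 subjects analysed as one cohort. None of the correlation, the alpha or the 9-week response rate is given. A reader might be tempted to quote 15 to 40 points as an unconditional cost. The documents do not support that: losses near 40 points need a response share well below either cited rate, pooling reduces the loss, and a threshold effect reverses it.

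The tests are exploratory, and no primary or secondary result changes. This is a cheap improvement to consider, not a flaw that must be corrected.

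**What to change.** In section 8.1, keep the planned responder versus non-responder Wilcoxon test. Beside it, prespecify a Spearman correlation (or the equivalent rank regression) of each marker with the percent change in the sum of target-lesion diameters from baseline to the preoperative scan. Give the worst rank to subjects with new lesions or non-target progression, and say how subjects without a preoperative scan are handled. State whether the analysis is by cohort or pooled. If the procedures manual already contains this analysis, name it in 8.1 instead. Leave the pathologic-response, one-year progression and PFS analyses as they are.

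The cost is one paragraph of wording, with no new subjects, scans or assays. The downside is one more exploratory test per marker and a ranking rule to define.

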### 8.1.1 Study Design

This is an open-labeled phase II study, in which eligible subjects with treatment-naïve, advanced RCC will be treated with perioperative pembrolizumab-based therapy prior to and after CN/MET. After safety lead in for each cohort, group sequential design will be applied for each combination cohort.

### 8.1.2 Randomization

This is a non-randomized study. Cohorts will be accrued concurrently.

### 8.1.3 Stratification Factors

There are no planned stratification factors.

## 8.2 Determination of Sample Size and Accrual Rate

### 8.2.1 Sample Size and Power Estimate

For the primary objective, there will be a binary classification. A subject will be considered to have a “positive response” if there is a  $\geq 2$ -fold increase (from pre- to post-treatment) in the number of TICCs, and a “negative response” if there is  $< 2$ -fold increase.

For Cohort A, with 12 subjects, if the true response rate is 30%, the 90% confidence interval of the response rate is (8%, 52%).

For each of the combination cohorts (cohorts B and C), the expanded part will be accrued based on group sequential design. In the first stage, 12 subjects (including the 6 subjects in safety lead-in) will be accrued at the dose level decided at safety lead in. If there are one or fewer responses in these 12 subjects, the study will be stopped due to futility, and if there are 5 or more responses,

the study will be stopped due to efficacy (one-sided alpha spending =0.0004). The final decision to terminate the cohort or continue accruing after these first 12 subjects will be based on discussion amongst members of the Joint Steering Committee, which is comprised of representatives for both Merck and the Sponsor. If accrual to the cohort is continued, additional subjects will be accrued for up to 36 evaluable subjects (or up to 30 if no dose reductions occur).

The null hypothesis of a 10% response rate will be rejected if 6 or more responses are observed in 30 subjects. This design yields a one-side type I error rate of 0.05 and power of 82.3% when the true response rate is 30%. Additionally, the first 6 subjects will be considered the “safety lead-in” for each cohort. If there are  $\geq 2$  DLTs in these first 6 subjects, then dose reduction will proceed as described in Section 5.1 and an additional 6 subjects will be accrued. The 6 subjects accrued as the safety lead-in are evaluable. Therefore, a minimum of 4, and a maximum of 36 subjects will be accrued to each pembrolizumab-based combination cohort.

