## 8.3 Interim Analyses and Stopping Rules

Each cohort will be stopped early for lack of safety, if the safety lead-in portion cannot be completed as outlined in the Study Design (Section 3).

The planned interim analysis for both futility and efficacy will be included based on group sequential design for the combination cohorts. 12 subjects (including the 6 subjects in safety lead-in) will be accrued at the dose level decided at safety lead-in. If there are one or fewer responses in these 12 subjects, the study will be stopped due to futility, and if there are 5 or more responses, the study will be stopped due to efficacy (one-sided alpha spending =0.0004). The final decision to terminate the cohort or continue accruing after these first 12 subjects will be based on discussion amongst members of the Joint Steering Committee, which is comprised of representatives for both Merck and the Sponsor.

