#### **8.4.2 Primary Analysis (or Analysis of Primary Endpoints)**

TIICs will be analyzed in pre- and post-pembrolizumab-based treatment tumor specimens. The proportion of subjects with a  $\geq 2$ -fold increase (from pre- to post-treatment) in the number of TIICs will be calculated.

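### The combination-cohort decision rule (12-subject interim, then 6 or more of 30) does not have the stated type I error of 0.05, power of 82.3% or interim alpha of 0.0004

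*Combined protocol and SAP*

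**What the plan says.** Section 8.2.1 defines a response as at least a doubling of tumor-infiltrating immune cells from the pre-treatment to the post-treatment specimen. For cohorts B and C it sets out a two-stage rule:

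- **First stage:** "In the first stage, 12 subjects (including the 6 subjects in safety lead-in) will be accrued". The cohort stops for futility at 1 or fewer responses.
- **Interim efficacy:** section 8.3 repeats the rule that "if there are 5 or more responses, the study will be stopped due to efficacy (one-sided alpha spending =0.0004").
- **Final analysis:** "The null hypothesis of a 10% response rate will be rejected if 6 or more responses are observed in 30 subjects".
- **Stated properties:** "This design yields a one-side type I error rate of 0.05 and power of 82.3% when the true response rate is 30" percent.

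Two qualifications are attached. On size, "additional subjects will be accrued for up to 36 evaluable subjects (or up to 30 if no dose reductions occur"), with a final cut-off printed for 30 only. On the interim, the stops are not binding, because "The final decision to terminate the cohort or continue accruing after these first 12 subjects will be based on discussion amongst members"; the body meant is the Joint Steering Committee.

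This is the only decision rule for the primary endpoint in these cohorts. Section 8.4.2 says only that the proportion with at least a doubling "in the number of TIICs will be calculated". The tests named in section 8.1 appear under the exploratory endpoints.

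**The concern.** The counts in the rule fix its operating characteristics completely once a true response rate is chosen, so the stated figures can be checked without any outside assumption. Six or more of 30 is a lenient cut-off against a 10% null, where 3 responses are expected. A level of 0.05 looked too low for it, and 82.3% also looked too low for the power. The stated interim spend looked too small for a boundary of 5 in 12.

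A cohort could be declared positive at a claimed one-sided 5% level that the rule does not meet. The committee would also be weighing an early efficacy stop while believing its false-positive probability to be 0.0004.

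**Working it through.** **Inputs** (all from section 8.2.1; the interim rule is repeated in 8.3): first stage 12; futility at 1 or fewer; efficacy at 5 or more; final cut-off 6 of 30, so 18 subjects in the second stage; null rate 0.10; alternative 0.30.

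**Formula.** With X1 ~ Bin(12, p) and X2 ~ Bin(18, p),

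P(reject) = P(X1 ≥ 5) + Σ over x = 2, 3, 4 of P(X1 = x) · P(X2 ≥ 6 − x).

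The terms for x = 0 and 1 are added when futility is overridden.

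**Both stops followed.**

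| First-stage result | p = 0.10 | p = 0.30 |
|---|---|---|
| 5 or more (stop, efficacy) | 0.00433 | 0.27634 |
| 2 | 0.23013 × 0.09820 = 0.02260 | 0.16779 × 0.83545 = 0.14018 |
| 3 | 0.08523 × 0.26620 = 0.02269 | 0.23970 × 0.94005 = 0.22533 |
| 4 | 0.02131 × 0.54972 = 0.01171 | 0.23114 × 0.98581 = 0.22786 |
| **Total** | **0.0613** | **0.8697** |

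The stated values are 0.05 and 0.823.

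**Committee discretion over the two printed stops.** Overriding futility adds 0.00181 + 0.01062 = 0.01243 at p = 0.10, and 0.00644 + 0.04750 = 0.05394 at p = 0.30.

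| Futility stop | Efficacy stop | Type I error | Power |
|---|---|---|---|
| followed | followed | 0.0613 | 87.0% |
| followed | overridden | 0.0608 | 86.9% |
| half overridden | followed | 0.0675 | 89.7% |
| always overridden | followed | 0.0738 | 92.4% |
| always overridden | overridden (single stage) | 0.0732 | 92.3% |

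None of these gives 0.05 or 82.3%.

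**Interim spend.** Under p = 0.10, P(X1 ≥ 5) = 0.00433, P(X1 ≥ 6) = 0.00054 and P(X1 ≥ 7) = 0.00005. The printed boundary spends 0.00433 / 0.0004 ≈ 11 times the stated amount, and no whole-number boundary in 12 subjects spends 0.0004.

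**Where the excess sits.** The probability of reaching the final analysis with exactly 6 of 30 under the null is 0.0365 with futility followed and 0.0462 with it overridden. Removing that outcome gives the cut-off of 7: 0.0613 − 0.0365 = 0.0249 (from unrounded values) with power 80.6%, or 0.0738 − 0.0462 = 0.0276 with power 84.3%.

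**Attempts to recover the stated figures.** A search over first stages of 8 to 17 and totals up to 40, for power 82.3% with type I error between 0.02 and 0.05, found no rule with 12 then 30 subjects. The only match with the printed cut-offs (1, 5, 6) was 11 then 28 subjects (0.0455 and 82.3%), which spends 0.0028 at the interim. Separately, the Lan-DeMets O'Brien-Fleming spending function at information fraction 12/30 gives 0.00039 for a one-sided level of 0.025, and 0.0019 for 0.05. Either might be a trace of the original design, but neither describes the printed rule, so the source of the figures stays open.

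**The case against.** The strongest objection concerns discretion. Section 8.2.1 lets the committee end or continue a cohort after 12 subjects and does not confine an ending to the two boundaries. If some cohorts with 2 of 12 were ended as well, both error and power would fall. Ending a third of them gives 0.0538 and 82.3%, ending half gives 0.0500 and 80.0%, and ending all gives 0.0387 and 73.0%. So 0.0608 and 86.9% are lower limits only for the follow-or-override scenarios tabulated. That limit on the claim stands. It does not restore the plan's figures: none of these three cases yields 0.05 and 82.3% together, none touches the interim 0.0004, and the plan presents its figures as properties of the printed design.

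The number analyzed could also fall short of 30, because section 8.4.1 requires evaluable paired specimens. With the same cut-offs, 28 subjects give 0.048 and 84.4%, and 27 give 0.042 and 82.7%. That is true, but the plan attaches its figures to 30.

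Finally, the excess error is modest (1.1 percentage points with both stops followed), power is better than claimed, and this is a small non-randomized phase II study. All of that is fair. The rule is nevertheless the only hypothesis test on the primary endpoint, and correcting the text needs no patients.

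**Conclusion.** The concern holds. For a 12-subject first stage and 30 subjects in total, the printed rule has a type I error of 0.061 and power of 87.0% with both stops followed, against the stated 0.05 and 82.3%. The upper limit is 0.074, with power 92.4%, and is reached only if every futility result is overridden. The interim efficacy boundary spends 0.0043, not 0.0004. A cohort declared positive on exactly 6 of 30 would not meet the claimed 5% level. The sample size is not too small for the printed rule.

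The result rests on exact binomial probabilities and the printed counts alone. It shows that rule and figures disagree, not which of them is misprinted. It does not extend to two other descriptions in the protocol. No final cut-off is printed for 36 subjects; carrying 6 over to 36 would give 0.106 with both stops followed. Section 5.1.2.1 describes 6 + 11 = 17 subjects after the lead-in rather than a first stage of 12.

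**What to change.** 1. Compare the printed boundaries with the original design output, name the software and method, and correct whichever of rule or figures was misprinted.
2. If the printed boundaries stand, restate sections 8.2.1 and 8.3 as type I error 0.061 with power 87.0% (futility binding), or up to 0.074 with 92.4% (futility non-binding). Give the interim alpha as 0.0043 in both cases and say which case applies. This changes wording in two sections and needs no extra patients; the cost is a less favorable stated error rate.
3. If the one-sided 5% level must be held with 30 subjects and this interim, the final cut-off would be 7 of 30: 0.025 and 80.6% binding, or 0.028 and 84.3% non-binding. This changes the decision rule of an open-label trial, so it should be made by amendment before the cohort's primary endpoint data are reviewed. With futility binding, its power is below both the stated 82.3% and the 87.0% of the printed rule. Its level is about half of what was intended.

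The same correction should state the final cut-off that applies if a cohort reaches 36 subjects, and reconcile the first-stage size with section 5.1.2.1.
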